### **8.2.2 Seventh Day after Injection (Day 8 ± 1)**

1. Study staff will confirm participant identity.
2. Study staff will review the participant Diary Card and interim history with the participant and inquire about any new medical events since medical histories were last updated. Any AEs that have occurred and meet reporting requirements, will be recorded in the appropriate section(s) of the CRF. Diary Card information will be entered into the database.
3. The participant will have temperature, pulse rate, and blood pressure recorded. A study clinician will perform a targeted (symptom based) physical examination and record the information Results will be reviewed by study staff and with the participant.
4. The participant will be instructed to inform the investigator as soon as possible if he/she experiences an AE requiring medical care and to seek medical care as appropriate. If the participant visits a health care provider, the participant should be sure to inform the

health care provider of participation in this study and give the health care provider the contact information for the investigator.

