Description of Agent or Intervention:	
Seasonal trivalent inactivated influenza vaccine (TIV), inactivated split virion, purified by sucrose gradient ultracentrifugation (IVAC, NhaTrang, Vietnam), or placebo (IVAC, Nha Trang, Vietnam). The vaccine will be produced in embryonated chicken eggs, and inactivated with formaldehyde. The dose of the vaccine to be tested is 15 mcg of each of the three components per 0.5 mL. The vaccine strains are
 

• NYMC BX-35 reassortant of B/Brisbane/60/2008 (B)

• NYMC X-179A reassortant of A/California/7/2009 (H1N1)

• NYMC X-263B reassortant of H3/A/Hong Kong/4801/2014 (H3N2)

 
Placebo is PBS with pH 7.2; 0.5 ml/per dose

Estimated Time to Complete Enrollment:	Approximate enrollment duration will be 3 weeks for phase 2 and 5 weeks for phase 3 study

Table 1: Schedule of events						
Study Activities	Study Day (# days from D1)					
	S1/D1* (up to -4/ D1 Clinic Visit	D1 to D7	D8 (+/- 1) Clinic Visit	D9 to D21	D22 (+/- 1) Clinic Visit	D91 (+/- 7) Telephonic contact
Information process and written informed consent	X					
Collect baseline demographic data	X					
Collect/review medical history	X					
Perform screening physical examination	X					
Perform vital signs & targeted physical examination (symptom based & reactogenicity only)	X*		X			
Perform urine pregnancy check (women)	X*					
Check/confirm inclusion/exclusion criteria	X*					
Randomization	X					
Collect serum for influenza serology	X**				X	
Administer one dose of study product (vaccine or placebo)	X					
Observe for 30 Minutes; record and manage immediate reactions	X					
Instruct participant on use of Dairy card	X					
Participant records solicited reactogenicity and unsolicited AEs in Dairy cards	X	X				
Clinical staff reviews interim AEs/SAEs with participant; records in CRF			X		X	SAE only
Report SAEs to Sponsor, IRBs and regulatory authorities	X	X	X	X	X	X
Participant completion of study						X
*If Day 1 is conducted on a different day from S1, eligibility must be confirmed again on Day of Injection (D1); including Targeted physical examination (PE); inclusion/exclusion; urine pregnancy test.						
** Sera samples will be collected prior to vaccination in phase 3 study at one site (Ben Luc).						

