### 3.2 Study Outcome Measures (Endpoints)

#### 3.2.1 Primary Endpoints

##### A. Primary Safety Endpoints, Phase 2 and 3

The number and proportion of participants reporting the following events:

- A. Solicited local adverse events, including redness / erythema, swelling / induration, pain within 30 minutes of vaccination and over a 7-day period (Days 1-7) post-vaccination.
- B. Solicited systemic adverse events, including fever, fatigue/malaise, muscle aches, joint aches, chills, nausea, vomiting, and headache within 30 minutes of vaccination and over a 7-day period (Days 1-7) post-vaccination.
- C. Unsolicited Adverse Events (AEs) occurring within 21 days post vaccination.
- D. Serious Adverse Events (SAE) occurring during the entire study period (Days 1-91).

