### **8.2.5 Final Study Visit (Day 91; $\pm$ 7)**

1. The participant will be contacted via telephone and identity confirmed.
2. Study staff will review interim medical histories and concomitant medications with the participant since these were last updated. No new concomitant medication will be recorded unless it relates to a newly identified SAE.
3. Study staff will ask about any medical event that would constitute an SAE since the last visit. No new AE information will be recorded unless it qualifies as an SAE.
4. If an SAE is reported, the clinician should record the SAE on the appropriate form, notify the entities who require notification, and refer the participant for treatment of the SAE, if warranted.

After recording the information, the participant will be discharged from the study.

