### 10.3 AE/SAE Reporting Period and Parameter

Safety events are reported from the time of study injection (Day 1) through completion of the study at Day 91. Specifically, solicited AEs to assess local and systemic reactogenicities will be collected at 30 minutes and then daily for 7 days thereafter. If a solicited AE starts during the 7 days post vaccination period and continues beyond the 7 days it will continue to be reported as a solicited AE. SAEs will be reported from Day 1 through the end of the study at Day 91. Unsolicited AEs will be reported from Day 1 to Day 22 inclusive.

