#### INSTRUCTIONS

1. Take your temperature by mouth each day using the thermometer we gave you.

- Start taking your temperature later today.
- Take it around the same time each day.
- Wait 15 minutes if you had a hot or cold drink.
- Insert the thermometer into your mouth under your tongue. Close your mouth.
- Wait for the beep or other indication that the temperature is ready.
- Write the temperature in the space on the Diary Card. If you take your temperature more than once during the day, write the highest temperature for the day on the Diary Card.

2. Each day, look at your arm where you received the injection.

- Check for redness and swelling. Touch your arm and feel for hardness at the injection site.
- If you do not find anything, check “None” on the diary card for the day.
- If you see or feel something, place a mark with a pen on either side of the area. Measure the widest part of it with the ruler we have given you.
- Record your measurement on the Diary Card. If you do more than one measurement during the day, record the largest measurement for each day on the Diary Card.
- Example: This person had redness at the injection site. They put dots with a pen at the widest points of the redness and measured it. It measured 2.4 cm. They wrote 2.4 cm on the Diary Card for that day.

3. Severity of symptoms:

- None: I did not have any discomfort
- Mild: I only had minor discomfort. I did my usual activities
- Moderate: I noticed the symptom. It bothered me enough that I did not do as much as I usually do
- Severe: I really noticed the symptom. It kept me from doing many of the things I wanted or needed to do

4. Please contact the study site using the number below if you have any questions:

Participant ID | | | | |

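### The Day 91 safety call may be made on Day 84 and ends follow-up, so SAEs on Days 85-91 need not be asked about; the Day 22 and Day 8 windows leave smaller gaps of the same kind

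*Combined protocol and SAP*

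**What the plan says.** Table 1 of the protocol, repeated as SAP Table 2, sets the closing contacts as "D8 (+/- 1) Clinic Visit", "D22 (+/- 1) Clinic Visit" and "D91 (+/- 7) Telephonic contact".

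- **Solicited reactions.** The endpoint covers Days 1-7 (protocol 3.2.1). Protocol 8.2.2 places the diary review at the Day 8 visit: "Study staff will review the participant Diary Card and interim history with the participant and inquire about any new medical events". Diary data are then entered into the database. For temperature, the diary card instructs: "Take it around the same time each day".
- **Unsolicited AEs.** Protocol 10.3 states: "Unsolicited AEs will be reported from Day 1 to Day 22 inclusive". Protocol 3.2.1 gives the period as 21 days after vaccination. Protocol 8.2.4 makes the Day 22 visit the AE close-out.
- **SAEs.** The endpoint in protocol 3.2.1 is "Serious Adverse Events (SAE) occurring during the entire study period (Days 1-91"), and SAP 17.2.3 tabulates SAEs for the same period. Under protocol 8.2.5 the final call records a new AE only if it is serious, and then: "After recording the information, the participant will be discharged from the study".

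SAP 6.5 applies no visit windowing and SAP 7.3 no imputation. Neither document appears to require a closing contact on or after the last day of its period, or a further contact after an early one.

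**The concern.** A window that extends to the left of the day on which a period closes allows the period to be closed before it is over. For SAEs this is final: the call is the last contact, it ends in discharge, and protocol 8.2.5 does not ask the participant to report anything afterwards.

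Nothing downstream would reveal it. Only contacts outside the window count as deviations (protocol section 17; SAP Appendix 1). The shell for the AE overview (Table 14.3.1.1) uses all subjects in the analysis population as denominator, so someone followed to Day 84 counts as event-free to Day 91.

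What is at stake is the match between the stated follow-up and the data. The safety case is a claim about absolute rates: protocol 13.3 says that zero related SAEs in 700 vaccinees would exclude a rate of about 0.43%.

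**Working it through.** **1. The plan's own figures (protocol 13.3).** Inputs: 740 randomised to vaccine, 5% drop-out, 700 evaluable, true rates of 0.33% and 0.43%.

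- Evaluable: 740 × 0.95 = 703 (plan: at least 700).
- P(at least one event) = 1 − (1 − p)^700. At p = 0.0033 this is 90.1% (plan: 90%); at p = 0.0043 it is 95.1% (plan: above 95%).
- Zero-event upper bound, one-sided 95%: 1 − 0.05^(1/700) = 0.427% (plan: about 0.43%).

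All three reproduce.

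**2. Window arithmetic.** Earliest contact = nominal day minus tolerance. Full days left = last day of period minus earliest contact.

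| Period | Ends | Earliest contact | Full days left | Share |
|---|---|---|---|---|
| Solicited | Day 7 | 8 − 1 = Day 7 | 0 | at most the rest of Day 7, one of seven diary entries |
| Unsolicited | Day 22 | 22 − 1 = Day 21 | 1 | 1/22 = 4.5% |
| SAE | Day 91 | 91 − 7 = Day 84 | 7 | 7/91 = 7.7% |

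Contacts on the nominal days leave no full day uncovered in any period.

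The unsolicited row needs one check, because 21 days after vaccination could be taken to end on Day 21, leaving no full day. The documents' day count points to Day 22: vaccination is Day 1, SAP 6.1 defines study day as the date difference plus one, and the sera due 21 days after vaccination are the Day 22 sera. That agrees with protocol 10.3.

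**3. Effect on SAE detection.** Assumption: uniform hazard over Days 1-91. Let f be the share called on Day 84. The documents do not give f, so the whole range is shown. The observable rate is p × (1 − f × 7/91).

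| f | p = 0.33% | p = 0.43% |
|---|---|---|
| 0 | 90.1% | 95.1% |
| 25% | 89.7% | 94.8% |
| 50% | 89.2% | 94.5% |
| 100% | 88.2% | 93.8% |

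At f = 100% the zero-event bound, rescaled to 91 days, is 0.427% × 91/84 = 0.46%. If vaccine-related SAEs occur before Day 84, f has no effect.

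**The case against.** The strongest reply is that early contact is permitted, not required, and that safeguards cover much of the rest.

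- **Diary.** A Day 7 visit loses at most the remainder of that day. Only the Day 1 column is labelled as evening, and the same-time instruction concerns temperature. The eCRF makes Day 7 temperature a required item and asks whether each reaction is ongoing after Day 7, with highest severity and end date. The card has its own collection date, and a separate monitoring form covers symptoms that continue. The Day 22 visit reviews interim events. This largely stands. It does not remove the possibility that the diary is reviewed and entered while the Day 7 entry is incomplete.
- **Unsolicited AEs.** Participants may report events at any time (protocol 10.1.2). What remains is a non-serious Day 22 event that nobody reports after a Day 21 visit; the later call cannot record it.
- **SAEs.** The effect on detection is small, the windows are the same in both blinded arms, and SAEs are not formally tested. All true, but none of it supplies the missing question for Days 85-91.

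A reader might infer that the last days of these endpoints go unobserved, or that the resolved/ongoing split at Day 7 is unreliable. The documents do not support either: the days are not systematically asked about only when a contact is early, spontaneous reporting stays open between visits, and ongoing reactions have their own follow-up.

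**Conclusion.** The point holds, mainly for the final call. A site that follows the protocol exactly can call on Day 84, discharge the participant and leave up to 7 of 91 SAE days unasked, while the endpoint and tables present Days 1-91 as followed. The Day 22 gap is one day of non-serious events, and the Day 7 gap is part of one day.

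The consequence is modest under-ascertainment of absolute rates. At worst, with every call on Day 84 and uniform hazard, detection falls by about 2 points at a 0.33% rate and just over 1 point at 0.43%; it is zero if related SAEs come earlier. The true size depends on the share contacted early and on when SAEs occur, and the documents give neither.

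Two stronger conclusions would go too far. One is that the comparison of vaccine with placebo is biased: the same windows apply to both arms under blinding. The other is that rates are known to be understated: nothing shows how often early contacts take place.

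**What to change.** - **Day 91 call.** In Table 1, protocol 8.2.5 and SAP Table 2, set the call on or after Day 91, for example 0/+14, which keeps the present width. Alternatively, keep the window and repeat the SAE question on or after Day 91 for anyone called earlier; this also serves calls already made.
- **Day 22 visit.** Leave the window unchanged, since moving it would shift the primary serology. Add a brief AE phone check on or after Day 22 for anyone seen on Day 21.
- **Day 8 visit.** For anyone seen on Day 7, have the participant complete the Day 7 diary page and return it or phone it in before data entry.
- **Reporting.** State how many contacts fell on Day 7, on Day 21 and on Days 84-90, so that the size of the gap is visible.

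The cost is a wording change and a few short calls. With 0/+14 the latest call moves from Day 98 to Day 105, a week later. That is still inside the planned lock, about four weeks after the last participant's Day 91 (roughly Day 91 + 28 = Day 119).

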### **8.2.3 Second and Third weeks after Injection (Days 9-21)**

There are no scheduled visits during this period. Participants may be asked to come to the study clinic if the investigator follows up on any laboratory or clinical issue. The participant will inform the study clinic of any medical events and seek medical care as needed. The participant will be instructed to give the contact information of the study investigator in case they consult any health care provider outside the study.

### **8.2.4 Final Visit (Day 22; $\pm$ 1)**

Day 22 is the last scheduled in-clinic visit for the participants for closing out AEs and reported medications (Phase 2 & Phase 3) and collection of immunogenicity samples for the Phase 3 portion of the study.

1. Study staff will confirm participant identity.
2. Phase 2 & 3: Study staff will review interim medical histories and concomitant medications with the participant since these were last updated. Results will be recorded in the appropriate section of the CRFs.
3. **Phase 3 only:** Blood specimens from participants who underwent blood collection at enrollment (S1/D1) will be collected for anti-influenza serologic assays. Specimen collection information must be documented on the CRF and in specimen collection logs. About 5 mL of blood will be collected.

### **8.2.5 Final Study Visit (Day 91; $\pm$ 7)**

1. The participant will be contacted via telephone and identity confirmed.
2. Study staff will review interim medical histories and concomitant medications with the participant since these were last updated. No new concomitant medication will be recorded unless it relates to a newly identified SAE.
3. Study staff will ask about any medical event that would constitute an SAE since the last visit. No new AE information will be recorded unless it qualifies as an SAE.
4. If an SAE is reported, the clinician should record the SAE on the appropriate form, notify the entities who require notification, and refer the participant for treatment of the SAE, if warranted.

After recording the information, the participant will be discharged from the study.

### **8.3 Early Termination Visit**

If a participant withdraws from the study for any reason prior to the planned study duration, every attempt is made to complete the following:

- Report of local and systemic reactogenicity and AEs are reviewed by PI (or designee).
- For participants (from one site in the phase 3) who withdraw from the study prior to scheduled immunogenicity laboratory testing, specimens are obtained for immunogenicity analysis if the participants agree to do so.
- Diary Card information is reviewed with the volunteer in detail by site staff, if in use since the last visit.
- Injection site(s) examination and a full physical examination are performed (if indicated).

IVAC must be informed within 48 hours of all instances of the premature termination of a participant's participation in the trial.

If the participant develops a reaction to study vaccine which the investigator believes threatens the participant's well-being, the withdrawn participant must be treated or transferred to a treatment facility.

### **8.4 Unscheduled Visits**

Participants may present to the study center during operating hours for an unscheduled visit should they experience any AE or if the participant's condition requires medical intervention. Data for any examinations or other procedures performed on the participant at an unscheduled visit must be recorded on the appropriate CRFs.

## **9 Study Evaluations**

### **9.1 Clinical Evaluations**

#### **9.1.1 Vital Signs**

- Temperature in degrees Celsius (recorded to the nearest 0.1 degree) will be measured by oral thermometer.
- Blood pressure in mm of mercury and pulse rates in beats per minute will be measured by automated device or manually

#### **9.1.2 Medical History**

At enrollment, medical histories must be thoroughly reviewed with the participant. The following medical conditions, in particular, will be assessed:

- Current or recent (within two weeks of enrollment) acute illness with or without fever.
- Recent vaccination history.
- Recent receipt of immune globulin or other blood products, or injected or oral corticosteroids or other immune modulator therapy within 3 months before enrollment.
- Hypersensitivity of any kind, but particularly to vaccines.
- Clinically relevant history of renal, gastrointestinal, hepatic, cardiovascular, hematological, dermatological, endocrine, neurological, pulmonary or immunological diseases.
- Seizures, including history of febrile seizures, or any other neurologic disorder.
- Known or suspected immunologic impairment of any kind.
- Known HIV infection.
- Known active TB disease.
- Alcohol or drug use.
- Concomitant medications that are ongoing (including trade name, dosing, indications, start date).
- For women, pregnancy, menstrual and contraceptive history and/or history of surgical sterility.

### 9.1.3 Physical Examination

#### General Physical Examinations

Qualified study clinicians will conduct a physical examination of all participants at S1/D1. This physical examination will include the following:

- Recording of general appearance
- Physical examination of all organ systems. This includes the following:
  - neurologic examination, including cranial nerve examination
  - chest auscultation
  - examination of lymph nodes (axillary and cervical)
  - heart auscultation
  - abdomen palpation (to check for liver size)
- Measurement of the following vital signs:
  - body temperature
  - blood pressure
  - pulse/heart rate

\* Grade 1 elevated blood pressure (140 to < 160 mmHg systolic OR 90 to < 100 mmHg diastolic) will not be considered to be exclusionary at screening, unless judged to be clinically significant by the PI.

#### Targeted Physical Examination

The targeted Physical examination focuses on symptoms reported by the participant and the presence or absence of local and systemic reactogenicity. If no symptoms are reported by the participant, the Targeted PE does not need to be performed. The exam will be made by a clinician on Day 1 (only if D1 is on a different day from S1) and Day 8. Evaluation must be made prior to administration of injection of study product if done on Day 1.

### 9.1.4 Injection Site Examination

Assessment of local Injection site reaction 30 minutes after vaccination will be done by trained study personnel and graded for severity according to the toxicity grading table in [Appendix A](#)

- Erythema /redness will be examined under proper lighting conditions and measured with a ruler if present.
- Swelling/induration will be examined by palpation and visual inspection under proper lighting conditions. The examiner may temporarily mark skin at margins of visible swelling/induration, then measure with a ruler the maximum diameter
- Pain will be assessed by (a) inquiring as to whether there is significant discomfort at rest and/or (b) whether movement of the injection site causes discomfort, impacts limb movement or daily activity.

## 9.2 Laboratory Evaluations

### 9.2.1 Clinical Laboratory Evaluations

#### Pregnancy Test

In order to confirm pregnancy status of females with potential to become pregnant, a qualitative human chorionic gonadotropin (hCG) test will be done on a urine sample. Pregnancy testing will be done on Day S1/D1, before vaccination. If Day S1 and D1 are conducted separately, the urine pregnancy test must be done on both visits. No injection of study product may be given to a woman without a pregnancy test being done and to any woman with a positive pregnancy test.

There are no safety laboratory tests in the study.

### 9.2.2 Special Assays

The HAI is the most frequently used serologic test for determining immunologic response to influenza vaccination. Serum specimens will be tested for the presence and titer of HAI antibodies to each one of the influenza strains represented in the vaccine. This testing will be performed by VisMederi srl laboratory, Siena, Italy, by using a validated assay. For these assays, serum specimen collection will occur on Days 1 and 22. Sample collection on Day 1 must occur prior to administration of study product.

### 9.2.3 Preparation, Processing, and Transport Specimens

#### Blood Specimens

Blood (serum) will be collected for HAI antibody serology.

#### Collection of Blood

Following universal precautions, blood will be collected from the forearm into tubes appropriate for collection of serum for HAI assay. Volumes of blood required for HAI assays at different time-points are shown in the [table](#) below.

	Collection Tube	Volume of blood	S1/D1 (pre-vac)	D22 (Last study visit)
Serum for anti-influenza serologic assays	Serum separator	5 mL tube	✓	✓

(The total volume of blood planned to be collected from each participant during the course of the study will be less than 15 milliliters.)

